9.8 Conversion Factors

The following conversion factors will be used to convert days into months or years:

• 1 week = 7 days, 1 month = 30.4375 days, 1 year = 365.25 days.

9.9 Date of Last Contact

The date of last contact will be derived for participants not known to have died at the analysis cut-off using the latest complete date prior to or at the data cut-off date among the following:

Participants on study treatment/during EFS follow-up

- AE start dates
- Date of last study treatment
- Date of last tumor assessment (eCRF form: CT scan or MRI)

Participants during survival follow-up

• Last known to be alive date collected on the Survival Follow-up eCRF page

Only dates associated with actual examinations of the participant reported in the eCRF will be used in the derivation. Assessment dates after the cut-off date will not be applied to derive the last contact date.

9.10 Time Window

Time window approach will not be used in this study.

9.11 Time on Study

Time on study, which will be used for IDMC output only, is defined in relation to the last assessment date at the time of data cut-off (considering last assessment date – randomization date +1).

The last assessment date is the last available assessment that indicates the patient is alive or dead. It includes end of study visit, safety assessment and/or phone call. If a participant dies, the last assessment date is the date of death.

9.12 Imputation of Missing Data

Unless otherwise specified, all data will be evaluated as observed, and no imputation method for missing values will be used.

Missing statistics, e.g., when they cannot be calculated, should be presented as "nd". For example, if n=1, the measure of variability (standard deviation [SD]) cannot be computed and should be presented as "nd".

Imputation rules for missing efficacy data are described in Section 14.

9.12.1 Partial and Missing Dates

All missing or partial dates will be presented in the participant data listing as they are recorded on the eCRF.

Adverse Events

In case the AE start date is missing or incomplete, the date will be imputed for the calculation according to the worst case approach. If the AE start date is completely missing it will be imputed with the first dose date. For incomplete AE start dates the missing day will be imputed by the first day of the month and the missing month will be imputed as January. If the imputed AE start date is prior to the first dose date, the AE start date will be set to the first dose date. Exceptions are given where the partial AE start dates would allow to state otherwise. Incomplete AE stop dates will be imputed by the last day of the month (if day is missing only), if not resulting in a date later than the date of participant's death. In the latter case, the date of death will be used to impute the incomplete AE stop date. In all other cases, the AE incomplete stop date will not be imputed.

Prior, Concomitant, and Subsequent Medications

In case the prior, and concomitant, or subsequent medication start date is partially missing, the day will be imputed by the first day of the month and the missing month will be imputed as January. For an incomplete stop date, the missing day will be imputed with the last day of the month, and the missing month will be imputed with December.

Dates of subsequent anticancer treatment

Incomplete start dates for the subsequent anticancer treatment will be imputed as follows and will be used for determining censoring dates for efficacy related sensitivity analyses:

• If only day is missing, it will be imputed as the first day of the month unless it results in a date before the last dose date. In that case, the incomplete anticancer treatment start date will be imputed as the last dose date.

• If both day and month are missing, the incomplete anticancer treatment start date will be imputed as the last dose date if the subsequent anticancer treatment started on the same year as the last dose date; otherwise, day and month will be imputed as the 1st of January.

Incomplete subsequent anticancer treatment stop dates will not be imputed.

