14.1 Primary Efficacy Endpoint: Event-free Survival (EFS)

Event-Free Survival (EFS) time is defined as the time (in months) from randomization to the first occurrence of any of the following events as assessed by the BIRC: death due to any cause, disease progression (radiological or clinical), primary treatment failure, relapse (radiological or clinical) or occurrence of a new cancer (see Table 1). Death as reported on the eCRF page "Death" will also be considered in the derivation of EFS time.

$$EFS = (date of EFS event - randomization date +1) / 30.4375$$

Censoring rules for the primary and sensitivity analyses of EFS are described in Table 4 below. The last adequate tumor assessment is defined as the last tumor assessment result that is not "Not evaluable" or "Not assessed". If a participant is meeting a multiple censoring situation, the earliest censoring criterion will be applied.

Table 4: Censoring rules for EFS

Situation	Primary	Sensitivity #1	Sensitivity #2
No evaluable baseline or post-baseline assessment*	Right censored at the date of randomization	Right censored at the date of randomization	Right censored at the date of randomization
Death, PD or any event entering in the definition of EFS after 2 or more consecutive missing or inadequate tumor assessments	Right censored at last adequate assessment before the consecutive missing/inadequate assessments	Right censored at last adequate assessment before the consecutive missing/inadequate assessments	Not applicable
Initiation of a new anticancer treatment for the disease under investigation before any event entering in the definition of EFS	Right censored at their last adequate assessment before the initiation of the new anticancer treatment	Not applicable	Not applicable
No death, PD, nor any event entering in the definition of EFS	Right censored at the date of their last adequate assessment	Right censored at the date of their last adequate assessment	Right censored at the date of their last adequate assessment

Abbreviations: EFS: Event-free survival; PD: Progressive disease

^{*}Any EFS event is considered as a post-baseline assessment.

Table 5: Estimand Attributes EFS

Objective	Estimand Attributes
Primary	

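### Incomplete start dates of new anticancer therapy are imputed early with no check against documented progression, and the stated scope leaves out the primary analyses that censor on them

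*SAP*

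**What the plan says.** SAP 9.12.1 has a dedicated rule for subsequent anticancer treatment:

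- Day missing: "If only day is missing, it will be imputed as the first day of the month unless it results in a date" earlier than the last dose, when the last dose date is used instead.
- Day and month missing, same year as last dose: "the incomplete anticancer treatment start date will be imputed as the last dose date if the subsequent anticancer treatment started on the same year".
- Day and month missing, any other year: "otherwise, day and month will be imputed as the 1st of January".

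These dates "will be used for determining censoring dates for efficacy related sensitivity analyses". The only floor is the last dose date.

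Two other places bear on the date. The general medication rule in 9.12.1 covers prior, concomitant and subsequent medication: "the day will be imputed by the first day of the month and the missing month will be imputed as January", with no floor. SAP 9.12 adds: "Imputation rules for missing efficacy data are described in Section 14". Section 14 gives no rule for therapy start dates.

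Table 4 lists the situation "Initiation of a new anticancer treatment for the disease under investigation before any event entering in the definition of EFS". Its Primary column reads: "Right censored at their last adequate assessment before the initiation of the new anticancer treatment". Both sensitivity columns mark the situation as not applicable. Tables 9 (PFS) and 11 (LRC) follow the same pattern. The Primary rule governs BIRC EFS, BIRC PFS and investigator LRC. It also governs the analyses labelled sensitivity: investigator EFS (Table 6), investigator PFS (Table 10) and BIRC LRC (Table 12). SAP 9.15 separately limits best overall response to scans made no later than the day new therapy starts.

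Protocol 1.3 places the EOT visit 15 (±7) days after the last study treatment and before any subsequent anticancer therapy. Protocol 7.1 requires study treatment to stop at progression.

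**The concern.** New systemic therapy or salvage treatment is usually a response to failure. Imputing its start to the earliest date the record allows, without looking at the failure date, can reverse the order. Under the Primary rule a reversed order matters: the participant is no longer an event at progression but is censored at the last adequate scan before the imputed date. The censoring is then informative, because it happens to participants who progressed.

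The scope sentence adds to the difficulty. Read against Table 4, it ties the imputed dates to sensitivity analyses, while the columns headed Sensitivity #1 and #2 do not censor for new therapy at all. The primary EFS, PFS and LRC analyses do use such a date and have no specific rule for it.

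**Working it through.** **1. Design figures.** Inputs from SAP Section 6 and Tables 2 and 3: looks at 279, 365 and 429 EFS events, HR 0.73, one-sided 0.025, Lan-DeMets O'Brien-Fleming-type spending, IA1 futility bound p = 0.163. The drift is √(events/4) × |ln HR|. At IA1 this is √(279/4) × 0.3147 = 2.628 against a boundary of z = 2.546, so power there is Φ(0.082) = 53.3%. With futility followed, the three looks give 53.3% + 25.8% + 9.2% = 88.3%; SAP Table 3 states 88.2%. The design reproduces.

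**2. Chance that the imputed start precedes progression.** Let L be the number of days from progression to the true start, with the true start spread evenly over the calendar.

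- Day missing, floor not binding: the order reverses when the day of the month exceeds L + 1. The share is about (30.4375 − L − 1)/30.4375.
- Day and month missing, year later than last dose: the share is about (365.25 − L − 1)/365.25.

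| L (days) | Day missing | 1 January |
|---|---|---|
| 7 | 74% | 98% |
| 14 | 51% | 96% |
| 28 | 5% | 92% |
| 60 | 0% | 83% |
| 90 | 0% | 75% |

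Calendar enumeration gave these values. As an example, L = 14 with the day missing gives 15.44/30.44 = 51%. With L spread over 0–30, 7–42 or 14–60 days, the day-missing share is 47%, 24% or 9%.

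**3. The last-dose branch.** Treatment stops at progression, so the last dose normally falls on or before it, and nearly every such record with a later progression reverses. After full treatment, C6D1 is day 106 (Protocol Table 1-1), so C6D14 is day 119 and EOT is 119 + 15 = day 134. An imputed start on day 119 precedes the first scheduled post-baseline scan. The last scheduled adequate assessment before it is baseline, and follow-up shrinks to about randomization. The imputed date also contradicts the Protocol 1.3 sequence, which puts EOT before any subsequent therapy.

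**4. How many events.** The documents give none of the inputs, so all are assumptions.

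- Share of EFS-event participants who start new therapy afterwards 30–60%, share of those with partial dates 2–10%, share reversed 8–90%. Low end: 429 × 0.30 × 0.02 × 0.08 = 0.2. High end: 429 × 0.60 × 0.10 × 0.90 = 23 (5.4%).
- Narrower case, 250 starters and day-missing dates only: 250 × 0.02 × 0.09 = 0.45 to 250 × 0.10 × 0.47 = 12.

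**5. Effect on power.** With the cut-off and z-boundaries fixed, losing 1%, 2%, 5% or 10% of events lowers power from 88.3% to 88.0%, 87.7%, 86.7% or 84.8%.

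**6. What cannot reverse.** Primary treatment failures are dated at randomization (Protocol 10.4.2). Deaths without prior new therapy are not exposed to the rule.

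**The case against.** The strongest reply concerns scope. The SAP relabels the Sensitivity #1 and #2 censoring schemes as supplementary analyses (Tables 5 and 7). Its own EFS sensitivity analysis in Table 6 is investigator-assessed EFS under Primary censoring. The sentence in 9.12.1 can therefore refer to analyses that do censor for new therapy. A reader might infer that the SAP applies the imputed dates to primary BIRC EFS; it does not say so. This stands. It does not settle the matter, because the primary analysis is then left with the general medication rule, which dates therapy as early or earlier.

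The second reply is that any effect would be small and visible. Supplementary analyses 1 and 2 ignore new therapy, censoring reasons are tabulated and listed, partial dates are listed as recorded, and data are queried before analysis. Because the analyses are triggered mainly by event counts, much of any loss would appear as delay. All of this stands as a limit on size. It makes a problem detectable but does not correct the confirmatory test.

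The third reply is that a floor at the event date has faults of its own. If deaths counted, therapy could be imputed after death. If the floor were the BIRC event date, therapy given on an earlier investigator-called progression could be moved past a later BIRC event, against the hypothetical strategy in Table 5. This stands, and it shapes the fix.

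**Conclusion.** The date rule needs correcting and its scope needs stating. Whether the 9.12.1 rule or the general medication rule is applied, a partial therapy date can be placed before the progression that prompted it, and the Primary rule of Tables 4, 9 and 11 then turns an event into a censoring at an earlier scan. The last-dose branch has the largest effect and conflicts with the protocol's visit order.

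The size is unknown and probably modest: below 1 to about 12 events in the narrower case, 0.2 to 23 of 429 in the wider one, and about 0 to 2 points of power. These figures rest wholly on assumed rates of new therapy, partial dates and reversal.

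A reader might go further and infer that the primary hazard ratio is biased, or that many events will be lost. The documents support neither. They give no frequency of partial dates, and in a double-blind trial nothing in them shows date completeness differing by arm. Bias would arise mainly if partial dates or use of new therapy did differ. Nor are participants censored at the moment of failure: Table 4 censors them at the last adequate assessment before therapy.

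**What to change.** Amend SAP 9.12.1 in two places.

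1. Scope: state that the imputed dates apply to every analysis using the Primary censoring rule (EFS, PFS and LRC, by BIRC or investigator) and to best overall response.
2. Rule: impute one start date per participant, as the latest of (a) the first day of the known month or year, (b) the last dose date and (c) the investigator-documented progression or relapse date, radiological or clinical but not death. Apply (c) only when it is compatible with the recorded partial date, and never impute a date after death. State that therapy imputed to the day of an event does not precede it, in line with the same-day convention in SAP 9.15.

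Using the investigator's date gives one therapy date across endpoints and leaves therapy before a later BIRC event where the estimand puts it.

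The cost is a short SAP edit and one derivation, fixed before unblinding; 429 events and 88.2% power are unchanged. Therapy truly begun earlier in the same month as the progression (or, for a year-only date, earlier in the same year) would be counted as following it. Supplementary analyses 1 and 2 already show the effect of that. A participant with no documented progression and a year-only date can still be assigned the last dose date, ahead of EOT. Such records should be queried, and the passages on imputation and EOT timing reconciled.

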9.12.2 Tumor assessments

All investigation dates (e.g., CT scan, MRI) must be completed with day, month and year.

If there are multiple scan dates associated with an evaluation, i.e., radiological assessments occur over a series of days rather than the same day, the choice of date of assessment could impact the date of progression and/or date of response. If there are multiple scan dates associated with an evaluation, the earliest of the scan dates associated with the evaluation will be used as the date of assessment.

If one or more investigation dates for an evaluation are incomplete but other investigation dates are available, the incomplete date(s) are not considered for calculation of the assessment date and assessment date is calculated as the earliest of all investigation dates (e.g., CT scan, MRI).

[figure not shown]
If all measurement dates for an evaluation have no day recorded, the 1st of the month is used.

If the month is not completed, for any of the investigations for an evaluation, the respective assessment will be considered to be at the date which is exactly between the previous and the following assessment. If both a previous and following assessments are not available, this assessment will not be used for any calculations.

9.12.3 Tumor Evaluation and Adjudication

Missing data from scheduled Tumor assessments not performed will not be imputed. Evaluable Tumor assessments are defined as those with overall response CR, PR, SD or PD for patients with measurable disease or CR, Non-CR/non-PD, or PD for patients with non-measurable disease only at baseline. Data from non-evaluable (NE) Tumor assessments will be used in the derivation of endpoints in accordance with Eisenhauer et al., (2009).

In case BIRC assessments are performed only the response assessments which are flagged as accepted after adjudication will be taken over to ADaM datasets and will be analyzed. In case of a missing adjudication flag for a response assessment and earliest image dates are equal, the assessment of reader 1 (the reader who completed baseline first) will be taken for analysis. Otherwise, the assessment for the reviewer who reviewed the record with the earliest image date will be analyzed. Analyses of tumor sizes will be based only on assessments of the reader whose assessment was accepted at baseline.

9.13 Unscheduled Assessments or Retests

Unscheduled assessments will not be used in the summary statistics per timepoint but will be used in the derivation of endpoints that are not related to a specific timepoint. All values collected will be displayed in the participant data listings.

9.14 Scoring of Health-Related Quality of Life (HRQL) Data

Unless otherwise specified, HRQL items will be scored using their published administration and most current scoring manual. For items with missing responses, the response will be managed as per the scoring manual.

9.15 Derivation of Best Overall Response

Best overall response will be assessed based on reported overall responses at different evaluation time points from randomization until documented disease progression in accordance to RECIST v1.1 as assessed by the BIRC or the investigator, respectively.

Only tumor assessments performed prior to the start of any subsequent anticancer treatment will be considered in the assessment of best overall response. If a tumor assessment was performed on the same day as the start of a new anticancer treatment, it will be assumed that the tumor assessment was performed prior to the start of the new anticancer treatment, therefore the tumor assessment will be included in the assessment of best overall response.

Best overall response (derivation):

- CR = at least one assessment of objective status of CR documented before progression.
- PR = at least one assessment of objective status of PR documented before progression (and not qualifying for CR).
- SD (applicable only to participants with measurable disease at baseline) = at least one SD assessment (or better) ≥ 6 weeks after randomization and before progression (and not qualifying for CR or PR).
- Non-CR/non-PD (applicable only to participants with non-measurable disease at baseline) = at least one non-CR/non-PD assessment (or better) ≥ 6 weeks after first dose date and before progression (and not qualifying for CR or PR).
- PD = progression latest at the time of the second scheduled post-baseline assessment, i.e., Day 1 of Month 7 plus 2 weeks (and not qualifying for CR, PR, SD or non-CR/non-PD). The condition PD in or out of the respective timeframe addresses a missing data situation in view of determining best overall response as PD or NE, respectively.
- NE: all other cases.

10 Study Participants

The subsections in this section include specifications for reporting participant disposition and study treatment/study discontinuations. Additionally, procedures for reporting protocol deviations are provided.

10.1 Disposition of Participants and Discontinuations

10.1.1 Screen Failures and Eligibility Criteria

Screen failures will be summarized overall based on all screened participants. The number of participants screened, and screen failures will be presented. In addition, the number and percentage of screen failures by reason will be displayed.

A participant data listing for all participants screened, along with whether the participant was a screening failure and if yes, the reason for the screen failure will be provided. Additionally, a second participant data listing will be provided showing whether the participant continued to meet eligibility to treatment prior to dosing, and if not, which eligibility to treatment was violated.

10.1.2 Participant Disposition

A participant is considered enrolled when randomized.

Participant disposition will be summarized by treatment arm and overall, for all participants based on Screened Set. The following will be summarized:

- Total number of participants screened (i.e., participants who gave informed consent).
- Number of randomized participants.
- Number of randomized participants who did not receive any study intervention.
- Number and percentage of participants who received at least one dose of any study intervention components.
- Number and percentage of treated participants who completed the treatment period.
- Number and percentage of treated participants who discontinued the treatment overall and by with the primary reason of discontinuation.
- Number and percentage of participants who continued into the EFS follow-up period.
- Number and percentage of participants who completed the EFS follow-up period until month 60 without EFS event.
- Number and percentage of participants who discontinued the EFS follow-up period overall and by primary reason for EFS follow-up period discontinuation.
- Number and percentage of participants who continued into the OS follow-up period.
- Number and percentage of participants who discontinued from study overall and by primary reason for study discontinuation.

Additionally, participant enrollment by country will be summarized by overall for all participants based on Screened set.

10.1.3 Time on Study

For IDMC only, time on study, as described in Section 9.11 will be summarized using descriptive statistics for continuous variables by treatment arm and overall based on the ITT set. In addition, Kaplan-Meier (KM) estimates (product-limit estimates) will be presented together with a summary of associated statistics as follows:

- Median time, Q1 and Q3 (whenever estimable) with their corresponding two-sided 95% Confidence Intervals (CIs) calculated according to Brookmeyer and Crowley (1982).
- The cumulative proportion of patients still in the study up to specific timepoints calculated using the reversed Kaplan-Meier methodology (Schemper & Smith 1996) where last assessment date is considered as an event and death is censored.

Graphical representation will be displayed with monotone increasing curves.

10.2 Protocol Deviations

Protocol deviations are categorized into:

- Non-important protocol deviations
- Important protocol deviations (IPDs)
- Clinically important protocol deviations (cIPDs)

IPDs are protocol deviations that might significantly affect the completeness, accuracy, and/or reliability of the study data or that might significantly affect a participant's rights, safety, or well-being.

IPDs include:

- Participants enrolled and dosed on the study who did not satisfy enrolment criteria
- Participants who are not compliant with treatment: overdose, dose modifications not as per protocol, incorrect dose, etc.
- Participants who receive a prohibited concomitant medication
- Failure to collect data necessary to interpret primary endpoints
- Failure to collect necessary key safety data
- Deviation from Good Clinical Practice (GCP)
- Any other protocol deviation that might significantly affect the completeness, accuracy, and/or reliability of the study data or that might significantly affect a participant's rights, safety, or well-being.

Important protocol deviations will be identified for all participants by either site monitoring, medical review processes or programming and confirmed prior to or at the Data Review Meeting at the latest.

IPDs are further classified into cIPDs which include, but are not limited to:

- Incorrect treatment group allocation, different to assignment at randomization.
- Incorrect stratification for randomization has been performed incorrect information entered (1:1 randomized by: Region (North America vs Western Europe vs Rest of the world), Primary tumor site (larynx vs other), Lymph node involvement (N0-1 vs N2 vs N3), T size (T4 vs other).
- Histologically confirmed diagnosis in LA SCCHN patient (stage III, IVA or IVB according to the American Joint Committee on Cancer [AJCC]/TNM Staging System, 8th Ed.) suitable for definitive CRT, of at least one of the following sites: oropharynx, hypopharynx, and larynx is not confirmed.
- Stage IVC (metastatic disease) Exclusion criteria 2
- Impaired cardiovascular function or clinically significant diseases, including any of the following:
 - Ongoing or history of uncontrolled or symptomatic ischemic myocardiopathy within 6 months prior to randomization.
 - Known left ventricular ejection fraction < 50%, left ventricular hypertrophy, ventricular arrhythmias, bradycardia (heart rate < 50 bpm).
 - History of myocardial infarction, or severe/unstable angina, within 6 months prior to randomization.
 - \circ New York Heart Association grade ≥ 3 congestive heart failure.
 - Symptomatic pulmonary disease requiring continuous or intermittent oxygen supply. Exclusion criteria 17
 - Non-compensated or symptomatic liver cirrhosis (Child-Pugh score: B or C). Exclusion criteria 21
- History of another malignancy within the last 3 years prior to randomization, with the
 exception of completely resected non-melanoma cell skin cancer outside the head and neck
 area or completely resected stage I breast cancer, or completely resected in-situ
 nonmuscular invasive bladder, cervix and/or uterine carcinomas or T1a squamous cell
 carcinoma of the esophagus. Exclusion criteria 18
- Missed baseline CT scan or MRI. Inclusion criteria 5
- Prior treatment for LA SCCHN
- Xevinapant/matched placebo relative dose intensity below 67% compared to the prescribed dose not due to a medical or safety reason
- Did not receive 200 mg/m2 or more of the overall planned cisplatin dose not due to a medical or safety reason

- Did not receive 66.5 Gy or more of the planned dose of the IMRT not due to a medical or safety reason
- Use of prohibited concomitant medication
- Any criterion identified during the Blind Data Review Meeting prior to database lock which may impact the efficacy analysis.

All protocol deviations are documented in the Study Data Tabulation Model (SDTM) domain DV. All important protocol deviations (including cIPDs) are documented in the Analysis Data Model (ADaM) domain ADDV whether identified for all participants by either medical review processes or programming, and confirmed prior to or at the Blind Data Review Meeting at the latest.

The cIPDs as well as the IPDs will be summarized by treatment arm and overall, for all participants in the ITT.

11 Demographics and Other Baseline Characteristics

